14.3 Secondary Efficacy Endpoints

The analyses of the secondary efficacy endpoints will be descriptive. Mean and associated 95% confidence interval will be provided for the following secondary endpoints, where the baseline value will be derived from the data in the approximately 12-month period prior to BMN 270 infusion:

- Change from baseline in the annualized utilization (IU/kg/year) of exogenous FVIII replacement therapy during Weeks 5-52 post-BMN 270 infusion, for subjects receiving FVIII prophylaxis during the 12 months prior to study entry, or change from baseline in the annualized utilization (mg/kg/year) of emicizumab during Week 27 to Week 52 post-BMN 270 infusion for subjects receiving prior emicizumab prophylaxis
- Change from baseline in the annualized infusion rate (number/year) of exogenous FVIII replacement therapy during Weeks 5-52 post-BMN 270 infusion, for subjects receiving FVIII prophylaxis during the 12 months prior to study entry, or change from baseline in the annualized utilization (mg/kg/year) of emicizumab during Week 27 to Week 52 post-BMN 270 infusion for subjects receiving prior emicizumab prophylaxis
- Change from baseline in the annualized number of bleeding episodes (number/year) requiring exogenous FVIII replacement treatment during Weeks 5-52 post-BMN 270 infusion for subjects receiving prior FVIII prophylaxis, or Weeks 27-52 post-BMN 270 infusion for subjects receiving prior emicizumab prophylaxis

Mean change from baseline and associated 95% confidence interval will be calculated for the total score of Haemo-QoL-A at Week 52 post-BMN 270 infusion as well.

The missing value of the change for annualized utilization and annualized infusion rate will be imputed as 0. The missing value of the change for annualized number of bleeding episodes will be imputed using the median value of the changes of all observed cases.

A sensitivity analysis is planned to analyze ABR using a generalized linear mixed model assuming negative binomial as the underlying distribution. The model will include period (pre- to post-BMN 270 infusion) as the only factor, repeated within subject. The actual number of bleeding episodes will be used as the dependent variable with the time period adjustment (annualization) being implemented as the offset.

To assess the impact of missing data, analyses using observed case are planned as sensitivity analyses for the secondary endpoints. Multiple imputation methods may also be performed.

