14.8 Determination of Sample Size

Approximately 20 subjects may be dosed in the study, including at least 16 subjects who are AAV5 antibody-negative and up to 25% of the total number of subjects who have an AAV5 antibody titer that is detectable but below the minimum required dilution at Screening. For the primary endpoint, a sample size of 16 will provide 85% power to demonstrate that the change in hFVIII activity during Weeks 49-52 from baseline is greater than 0, assuming an effect size of 0.8, using a one-sample t-test at the 1-sided significance level of 0.025 (or

equivalently, at the 2-sided significance level of 0.05). The effect size of 0.8 is assumed conservatively based on the results from 270-201 and the interim results from 270-301.

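### If any change in bleeding rate is missing, filling it with the observed median makes the reported 95% CI too narrow

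*Protocol*

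**What the plan says.** Protocol Section 14.3 sets the summary for the use and bleeding endpoints: "Mean and associated 95% confidence interval will be provided for the following secondary endpoints". It fixes two different rules for missing values. For factor VIII consumption, "The missing value of the change for annualized utilization and annualized infusion rate will be imputed as 0". For bleeding episodes, the missing change "will be imputed using the median value of the changes of all observed cases".

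The section also states that "The analyses of the secondary efficacy endpoints will be descriptive". It plans a negative-binomial mixed model for ABR as a sensitivity analysis, using actual counts with an offset for time. On missing data, "analyses using observed case are planned as sensitivity analyses for the secondary endpoints", and "Multiple imputation methods may also be performed".

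Section 14.8 plans for about 20 dosed subjects, "including at least 16 subjects who are AAV5 antibody-negative". Section 14.9 makes the antibody-negative subjects the primary efficacy population. Section 9.3.4 does not replace subjects who withdraw after dosing.

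This wording of Section 14.3 comes from the original protocol of 28 February 2020. Section 14.3 of Amendment 1 (15 September 2020) is not in the text supplied, and the amendment's summary lists no change to the rule.

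**The concern.** The first issue is precision. A single constant at the centre of the observed changes is treated as if it had been measured. The sample size goes up, the sum of squares hardly moves, and both the standard deviation and the standard error shrink. With no test on this endpoint, the mean and its interval carry all of its inferential content, so an interval that looks more precise than the data allow is a real defect.

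The second issue is consistency. Inclusion criterion 2 (Section 9.3.1) requires a documented 12-month history, so the missing part of a change is the on-study part. For prior-FVIII subjects the windows for use and bleeding are both Weeks 5-52. A subject lost before that window opens is given no reduction in factor VIII use, but the median reduction in bleeds that needed factor VIII. The section does not explain why the same lost subject is treated in two ways.

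**Working it through.** **The plan's own figure.** None is stated for ABR or for the amount of missing data. The one related figure, 85% power for the primary endpoint, reproduces: the noncentral t with 15 df and noncentrality 0.8 × √16 = 3.2 gives 84.8%. It is unaffected by this rule.

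**Inputs.** N = 16 is the minimum antibody-negative number in Section 14.8. The number missing, k, is an assumption, so a range is shown. The number observed is m = N − k.

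**Interval width.** If the imputed value equals the observed mean, the sum of squares does not change:

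- SD(imputed) = SD(observed) × √((m−1)/(N−1))
- SE ratio = √((m−1)/(N−1)) × √(m/N)
- Half-width ratio = SE ratio × t(.975, N−1) / t(.975, m−1)

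If the median differs from the mean, the sum of squares grows only by (mk/N) × (median − mean)².

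**Coverage.** With normal changes missing independently of outcome, coverage = P(|T| ≤ t(.975, N−1) × SE ratio), where T has m−1 df and t(.975, 15) = 2.131.

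| k | m | SE ratio | t ratio | Half-width ratio | Narrower by | Coverage |
|---|---|---|---|---|---|---|
| 1 | 15 | 0.966 × 0.968 = 0.935 | 2.131/2.145 = 0.994 | 0.930 | 7% | P(abs T ≤ 1.994), 14 df = 93.4% |
| 2 | 14 | 0.931 × 0.935 = 0.871 | 2.131/2.160 = 0.987 | 0.859 | 14% | P(abs T ≤ 1.856), 13 df = 91.4% |
| 3 | 13 | 0.894 × 0.901 = 0.806 | 2.131/2.179 = 0.978 | 0.789 | 21% | P(abs T ≤ 1.718), 12 df = 88.9% |

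Simulation with the actual sample median gives 93.5%, 91.2% and 88.8%. For all subjects (N = 20), the half-width ratios for k = 1, 2, 3 are 0.945, 0.890 and 0.835.

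**Count-like data.** Assumed negative-binomial bleeds, mean 4 per year before and 1 after, missing independently of outcome, N = 16, k = 2, 40,000 replicates:

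| Assumed skew | Coverage, median rule | Coverage, observed cases |
|---|---|---|
| Milder | 91.1% | 94.8% |
| Strong | 87.6% | 91.6% |

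The baseline mean of 4 is the top of the range of medians (1-4) that Section 7.3 cites for prophylaxis. Under strong skew part of the shortfall exists before any imputation, so the observed-case column is the fair comparator.

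**Direction of the estimate (strong skew, k = 2).** The median-imputed mean is −2.85 and the observed-case mean is −3.01. If the two lost subjects truly had no change, the true mean is −2.62, and the imputed mean overstates the reduction by 2.85 − 2.62 = 0.23 bleeds per year. Observed cases, at −3.00, overstate it more.

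**Would imputing 0 repair the interval?** A separate simulation with strongly skewed counts and the same means (N = 16, k = 2) gave half-widths of 2.11 with 0, 2.04 with the median and 2.36 with observed cases. The 0 rule is therefore still 1 − 2.11/2.36 = 11% narrower than observed cases. Coverage was 88.2%, 88.7% and 92.7%. If lost subjects truly had no change, 0 did better than the median (93.1% against 91.4%).

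**The case against.** The strongest reply is that the problem may never arise. ABR can be annualized from partial follow-up, so a change is probably missing only when a subject contributes nothing inside the window; Section 14.3 does not say this, but it is the natural reading. Visits are weekly to Week 26. Section 7.4 of Amendment 1 reports 151 subjects dosed across the programme with no discontinuation because of an adverse event, although other reasons are not given. Nothing in the document supports a particular number missing. This stands, and it limits the claim to a conditional one. The exposure is greatest for prior-emicizumab subjects, whose window opens only at Week 27.

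The second reply is that the same section already mitigates the fault. Observed-case analyses remove the false precision, and no imputation of the change is described for the negative-binomial model. This also stands, but both are sensitivity analyses and the median-filled interval remains the main result.

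Third, a reader might infer that the rule inflates the estimated benefit. The documents do not support that as a general statement. With skewed changes the median is smaller in size than the mean, and the filled-in estimate can be less favourable than the observed-case estimate (−2.85 against −3.01). The rule credits more benefit than a change of 0, but that is a choice of missing-data assumption and not in itself an error.

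A reader might also infer that the reported interval is bound to miss its nominal coverage, or that a significance claim is at risk. Neither follows: with no missing changes the rule does nothing, and the endpoint carries no test.

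**Conclusion.** The point holds in conditional form. If at least one ABR change is missing, the main 95% interval in Section 14.3 is too narrow by construction: by 7%, 14% or 21% for 1, 2 or 3 missing of 16. Coverage is then about 93%, 91% or 89% under normal changes missing independently of outcome, and lower with strongly skewed counts. The numbers missing and the count distributions are assumptions. The two imputation rules in one paragraph also make opposite assumptions about a subject lost to both endpoints, without a reason.

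The rule is fixed in the protocol and is not a detail left open for the SAP, although Section 14.1.2 defers further missing-data detail there. The primary endpoint is unaffected. The change is worth making because it is cheap and because this interval is the endpoint's main result. One caveat remains: the rule is read from the original protocol, and its survival in Amendment 1 is likely but not confirmed.

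**What to change.** In Section 14.3, drop the median rule for the main ABR summary. Take the mean change and 95% CI from multiple imputation, turning "Multiple imputation methods may also be performed" into a commitment for ABR, or from observed cases. Name one of the two as the main analysis. Keep the planned negative-binomial model.

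Add a change of 0 for lost subjects as a conservative sensitivity analysis. It matches the rule that "annualized utilization and annualized infusion rate will be imputed as 0" and shows the result if loss means no benefit, which observed cases alone would not. It should not become the main rule, because it is also a single constant with n counted as complete and does not restore the interval width.

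The cost is a few sentences in Section 14.3 and matching SAP text, with no change to data collection. The downside is a wider interval if anyone is missing. Check first that Section 14.3 of Amendment 1 still carries the rule.

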14.4 Tertiary Efficacy Endpoints

The analyses of the tertiary efficacy endpoints will be descriptive. Mean change from baseline and associated 95% confidence interval will be provided for EQ-5D-5L, WPAI+CIQ: HS and PROBE scores at Week 52 post-BMN 270 infusion.

14.5 Immunogenicity

Analysis of total and neutralizing antibody response and other immunological parameters will be primarily descriptive and involve both inter-subject and intra-subject comparisons.

14.6 Pharmacodynamic Analyses

Plasma FVIII protein concentrations and FVIII activities determined over the course of the study will primarily be evaluated and summarized with descriptive statistical measures (eg, mean, standard deviation, CV%, min, median, max).

14.7 Safety Analysis

All AEs will be coded to system organ class and preferred term using the current version of MedDRA. The incidence of AEs will be summarized by system organ class, preferred term, relationship to study drug, seriousness, and severity. A by-subject listing will be provided for those subjects who experience an SAE, including death, EOSI, or an AE resulting in early withdrawal from the study.

Clinical laboratory data will be summarized by the type of laboratory test. For each clinical laboratory test, descriptive statistics will be provided on Baseline as well as all subsequent visits. Descriptive statistics for physical examination results and vital signs will also be provided.

Detailed statistical methods will be provided in the SAP.

14.8 Determination of Sample Size

Approximately 20 subjects may be dosed in the study, including at least 16 subjects who are AAV5 antibody-negative and up to 25% of the total number of subjects who have an AAV5 antibody titer that is detectable but below the minimum required dilution at Screening. For the primary endpoint, a sample size of 16 will provide 85% power to demonstrate that the change in hFVIII activity during Weeks 49-52 from baseline is greater than 0, assuming an effect size of 0.8, using a one-sample t-test at the 1-sided significance level of 0.025 (or

equivalently, at the 2-sided significance level of 0.05). The effect size of 0.8 is assumed conservatively based on the results from 270-201 and the interim results from 270-301.

14.9 Analysis Populations

The intention-to-treat (ITT) population is defined as all subjects who received BMN 270 infusion. The ITT population will be the primary population for safety analyses, as well as being used for supportive efficacy analyses.

The modified intention-to-treat (mITT) population is the primary analysis population for efficacy for this study. The mITT population will include all subjects who received BMN 270 infusion and who were AAV5 antibody negative at Screening (ie, excludes subjects with an AAV5 antibody titer detectable but below the minimum required dilution).

Subjects with an AAV5 antibody titer detectable but below the minimum required dilution will be used for exploratory efficacy analysis on FVIII activity, as measured by chromogenic substrate assay, during Weeks 49-52 post BMN 270 infusion.

14.10 Changes in the Conduct of the Study or Planned Analyses

Only BioMarin may modify the protocol. Any change in study conduct considered necessary by the Investigator will be made only after consultation with BioMarin, who will then issue a formal protocol amendment to implement the change. The only exception is when an Investigator considers that a subject's safety is compromised without immediate action. In these circumstances, immediate approval of the chairman of the IRB/IEC must be sought, and the Investigator should inform BioMarin and the full IRB/IEC within 2 working days after the emergency occurs.

With the exception of minor administrative or typographical changes, the IRB/IEC must review and approve all protocol amendments. Protocol amendments that have an impact on subject risk or the study objectives, or require revision of the ICF, must receive approval from the IRB/IEC prior to their implementation.

When a protocol amendment substantially alters the study design or the potential risks or burden to subjects, the ICF will be amended and approved by BioMarin and the IRB/IEC, and all active subjects must again provide informed consent.

15 DATA MONITORING COMMITTEE

An independent DMC will be convened for this study. The duties of the DMC will include:

- Conducting an ongoing review of individual subject safety and efficacy data during the study.
- Recommending whether to continue enrolling subjects based on emerging data and the overall risk/benefit analysis of BMN 270.
- Making other recommendations on the conduct and reporting of the trial based on their evaluation of clinical data.

Details on the composition of the committee, frequency of meetings, and other committee functions and parameters are included in the DMC Charter and in the SAP.

16 COSTS, COMPENSATION, AND SUBJECT INJURY

There will be no charge to study subjects to be in this study. BioMarin will pay all costs of tests, procedures, and treatments that are part of this study. In addition, after IRB/IEC approval, BioMarin may reimburse the reasonable cost of travel for study-related visits in accordance with BioMarin's travel and reimbursement policy. BioMarin will not pay for any hospitalizations, tests, or treatments for medical problems of any sort related solely to the study subject's disease. Costs associated with such hospitalizations, tests, and treatments should be billed and collected in the way that such costs are usually billed and collected outside the study.

The Investigator should contact BioMarin immediately upon notification that a study subject has been injured by the study drug or by procedures performed as part of the study. Any subject who experiences a study-related injury should be instructed by the Investigator to seek immediate medical treatment at a pre-specified medical institution if possible, or at the closest medical treatment facility if necessary. The subject should be given the name of a person to contact to seek further information about, and assistance with, treatment for study-related injuries. The treating physician should bill the subject's health insurance company or other third party payer for the cost of this medical treatment. If the cost of the medical treatment is not covered by health insurance or another third party that usually pays these costs, then either BioMarin or the institution may pay for reasonable and necessary medical services to treat the injuries caused by the study drug or study procedures. In some jurisdictions, BioMarin is obligated by law to pay for study-related injuries without prior recourse to third party payer billing and/or regardless of fault. If this is the case, BioMarin will comply with the law.

17 CASE REPORT FORMS AND SOURCE DOCUMENTS

Electronic case report forms will be provided for each subject. The Investigator must review and electronically sign the completed eCRF casebook to verify its accuracy.

eCRFs must be completed using a web-based application developed and validated. Study site personnel will be trained on the application and will enter the clinical data from source documentation. Unless explicitly allowed in the eCRF instructions, blank data fields are not acceptable.

In the event of an entry error, or if new information becomes available, the value will be corrected by deselecting the erroneous response and then selecting or entering the factual response. In compliance with ICH GCP Guidelines and 21 CFR Part 11, the system will require the personnel making the correction to enter a reason for changing the value. The documented audit trail will include the reason for the change, the original value, the new value, the date and time of the correction and the identity of the operator.

BioMarin's policy is that study data on the eCRFs must be verifiable to the source data, which necessitates access to all original recordings, laboratory reports, and subject records. In addition, all source data should be attributable (signed and dated). The Investigator must therefore agree to allow direct access to all source data. Subjects must also allow access to their medical records, and subjects will be informed of this and will confirm their agreement when giving informed consent. If direct source document verification of study data by the site monitor is prohibited by institutional policy or local law, then the Investigator must make available facilities and/or personnel to allow GCP-compliant source verification to occur. Examples of such methods include certified copies of records which have study data visible but sensitive information redacted, or other GCP-compliant means agreed between the Investigator and the Sponsor.

A site monitor designated by BioMarin will compare the eCRFs with the original source documents at the study site and evaluate them for completeness and accuracy before designating them as "Source Data Verified" (SDV). If an error is discovered at any time or a clarification is needed, the site monitor, or designee, will create an electronic query on the associated field. Site personnel will then answer the query by either correcting the data or responding to the query. The site monitor will then review the response and determine either to close the query or re-query the site if the response does not fully address the question. This process is repeated until all open queries have been answered and closed.

Before a subject's eCRF casebook can be locked, data fields must be source data verified and all queries closed. Refer to the Study Monitoring Plan for details on which fields must be

source data verified. The Investigator will then electronically sign the casebook, specifying that the information on the eCRFs is accurate and complete. The Data Manager, or designee, will then set the status of the forms, visits, and the entire casebook to Locked. Upon completion of the CSR, an electronic copy of each site's casebooks will be copied to a compact disk (CD) and sent to each site for retention with other study documents.

18 STUDY MONITORING AND AUDITING

Qualified individuals designated by BioMarin will monitor all aspects of the study according to GCP and standard operating procedures for compliance with applicable government regulations. The Investigator agrees to allow these monitors direct access to the clinical supplies, dispensing, and storage areas and to the clinical files, including original medical records, of the study subjects, and, if requested, agrees to assist the monitors. The Investigator and staff are responsible for being present or available for consultation during routinely scheduled site visits conducted by BioMarin or its designees.

Members of BioMarin's GCP Compliance Department or designees may conduct an audit of a clinical site at any time before, during, or after completion of the study. The Investigator will be informed if an audit is to take place and advised as to the scope of the audit.

Representatives of the FDA or other Regulatory Agencies may also conduct an audit of the study. If informed of such an inspection, the Investigator should notify BioMarin immediately. The Investigator will ensure that the auditors have access to the clinical supplies, study site facilities, original source documentation, and all study files.

19 RETENTION OF RECORDS

The Investigator must retain all study records required by BioMarin and by the applicable regulations in a secure and safe facility. The Investigator must consult a BioMarin representative before disposal of any study records, and must notify BioMarin of any change in the location, disposition or custody of the study files. The Investigator /institution must take measures to prevent accidental or premature destruction of essential documents, that is, documents that individually and collectively permit evaluation of the conduct of a study and the quality of the data produced, including paper copies of study records (eg, subject charts) as well as any original source documents that are electronic as required by applicable regulatory requirements.

All study records must be retained for at least 2 years after the last approval of a marketing application in the US or an ICH region and until (1) there are no pending or contemplated marketing applications in the U.S. or an ICH region or (2) at least 2 years have elapsed since the formal discontinuation of clinical development of the IP. The Investigator /institution should retain subject identifiers for at least 15 years after the completion or discontinuation of the study. Subject files and other source data must be kept for the maximum period of time permitted by the hospital, institution or private practice, but not less than 15 years. These documents should be retained for a longer period, however, if required by the applicable regulatory requirements or by a BioMarin agreement. BioMarin must be notified and will assist with retention should Investigator /institution be unable to continue maintenance of subject files for the full 15 years. It is the responsibility of BioMarin to inform the Investigator /institution as to when these documents no longer need to be retained.

